### 3.3 Inclusion of Women and Minorities

Both men and women of all races and ethnic groups are eligible for this trial.

## 4. TREATMENT PLAN

### 4.1 Agent Administration

- 4.1.1 Study Treatment: all subjects will receive the following:

**Table 1: Regimen Description**

REGIMENT DESCRIPTION					
Agent	Premedication	Dose	Route	Frequency	Cycle Length
Nivolumab	No prophylactic pre-medication will be given unless indicated by previous experience in an individual subject per Section 5.5	240 mg	IV over 30 minutes*	Every 2 weeks	6 weeks (42 days)
Ipilimumab	No prophylactic pre-medication will be given unless indicated by previous experience in an individual subject per Section 5.5	1 mg/kg	IV over 30 minutes*	Every 6 weeks	

\*Infusion times are approximate (+/- 10 min) and may be adjusted based on subject tolerability.

- 4.1.2 Cycle length

One cycle is defined as 42 days.

#### 4.1.3 Dosing

Nivolumab and ipilimumab will be administered on the same day. Separate infusion bags and filters must be used for each infusion. Nivolumab is to be administered first. The second infusion will always be ipilimumab and will start no sooner than 30 minutes after completion of the nivolumab infusion. Subjects who require small volumes may infuse over < 60 minutes but no less than 20 minutes.

Nivolumab and ipilimumab may be diluted in 0.9% Sodium Chloride Solution or 5% Dextrose solution.

Dosing calculations for ipilimumab should be based on the body weight. If the subject's weight on the day of dosing differs by > 10% from the weight used to calculate the prior dose, the dose must be recalculated. All doses should be rounded to the nearest milligram. There will be no dose modifications allowed.

Subjects may be dosed with nivolumab no less than 12 days from the previous dose. There are no premedications recommended.

Doses of nivolumab and/or ipilimumab may be interrupted, delayed, or discontinued depending on how well the subject tolerates the treatment. For more details, see **Section 5.2** (dose delays).

### 4.2 General Concomitant Medication and Supportive Care Guidelines

#### 4.2.1 Prohibited and/or Restricted Treatments

- 4.2.1.1 Systemic immunosuppressive agents are prohibited during the study, unless they are utilized to treat an adverse event. Allopurinol to prevent gout flares is allowed.
- 4.2.1.2 Concurrent administration of any anti-cancer therapies (investigational or approved) is also prohibited with the exception of subjects in the survival period of the study. This includes somatostatin analogues.
- 4.2.1.3 Any medicinal herbal preparation unless prescribed by the treating physician. All concomitant medications including prescribed medicinal herbal preparations must be documented.
- 4.2.1.4 G-CSF (granulocyte-colony stimulating factor) will be permitted. However, the use of these agents is allowed as per their respective label indications/institutional guidelines to treat neutropenia that occurs on study. G-CSF must not be used for the treatment of cancer or for any primary prophylaxis while on study.
- 4.2.1.5 Any non-oncology live viral vaccine therapies used for the prevention of infectious diseases within 12 weeks prior to study drug is prohibited. The use of the inactivated seasonal influenza vaccine will be permitted on study without restriction.

4.2.1.6 Alcohol consumption while on study is strongly discouraged due to the potential to confound interpretation of hepatotoxic events.

4.2.1.7 Routine use of acetaminophen use is strongly discouraged

#### 4.2.2 Permitted Therapy

4.2.2.1 Regular concomitant use of bisphosphonates and RANK-L inhibitors for prevention or reduction of skeletal-related events in patients with bone metastases is allowed if initiated prior to first dose of study therapy.

4.2.2.2 Subjects are permitted the use of anti-emetic medications (with the exception of dexamethasone and/or other systemically administered steroids) at the treating physician's discretion.

4.2.2.3 Subjects are permitted the use of full-dose anti-coagulation (i.e. warfarin, enoxaparin, rivaroxaban, etc.) at the treating physician's discretion.

4.2.2.4 Subjects are permitted the use of topical, ocular, intra-articular, intranasal, and inhalational corticosteroids (with minimal systemic absorption).

4.2.2.5 Adrenal replacement steroid doses  $\leq$  10 mg daily prednisone are permitted.

4.2.2.6 A brief (less than 2 weeks) course of corticosteroids for prophylaxis (e.g., contrast dye allergy) or for treatment of non-autoimmune conditions (e.g., delayed-type hypersensitivity reaction caused by a contact allergen) is permitted.

4.2.2.7 Palliative local therapy, including palliative radiation therapy- and palliative surgical resection, is permitted prior to discontinuation of study treatment for subjects who do not have evidence of overall clinical or radiographic progression per RECIST 1.1.

Subjects requiring palliative local therapy should be evaluated for objective evidence of disease progression prior to the initiation of such therapy, particularly if the most recent tumor assessment was more than 4 weeks prior to the start of local therapy. If progression per RECISTv1.1 is identified on any tumor assessments prior to the initiation of palliative local therapy, then subjects must either discontinue study drug treatment or they must meet criteria to continue treatment beyond progression (**Section 5.3**) in order to resume immunotherapy after palliative local therapy.

The potential for overlapping toxicities with radiotherapy and nivolumab plus ipilimumab currently is not known; however, anecdotal data suggests that it is tolerable. As concurrent radiotherapy and nivolumab /ipilimumab have not been formally evaluated, in cases where palliative radiotherapy is required for a tumor lesion, then nivolumab /ipilimumab should be withheld for at least 1 week before, during, and 1 week after radiation. Subjects should be closely monitored for any potential toxicity during and after receiving radiotherapy, and AEs should resolve to Grade  $\leq$  1 prior to resuming nivolumab or ipilimumab.

#### **4.3 Dosing Criteria**

To account for drug quantities supplied within each vial and to minimize wasted unused investigational drug, pharmacy may adjust the calculated drug dose +/- 10% for each patient. All patients dosed within these parameters will be considered dosed at full dose.

#### **4.4 Definition of an Overdose for this Protocol**

Patients dosed > 10% above their calculated drug dose will be considered over-dosed.

#### **4.5 Contraception, Use in Pregnancy, Use in Nursing**

See Section 3.2.8

#### **4.6 Duration of Therapy**

Treatment will be continued for up to 2 years or discontinuation due to toxicity, withdrawal of consent, or study closure. Subjects may discontinue either drug and remain on the other agent if certain circumstances are met ([Section 5.2.7](#)).

#### **4.7 Off Study/Safety Follow-up Visit**

The post-treatment follow-up begins when the decision to discontinue a subject from all treatment is made.

Subjects who discontinue treatment for reasons other than disease progression will continue to have tumor assessments (if clinically feasible) according to the schedule in [Section 9](#) until progression is confirmed.

Subjects will be followed for drug-related toxicities until these toxicities resolve, return to baseline or are deemed irreversible. All adverse events will be documented for a minimum of 100 days after the last dose of study medication.

#### **4.8 Duration of Follow Up**

After completion of the first two follow-up visits, subjects will be followed every 3 months for survival until death, withdrawal of consent, or study closure. Survival follow-up visits may be performed by phone or email contact or office visit ([Section 9](#)). At that time of this request, each subject will be contacted to determine their survival status unless the subject had withdrawn consent for all contact.

Study assessments are to be collected as outlined in study calendar in [Section 9](#).

#### **4.9 Criteria for Removal from Study Treatment**

Patients will be removed from the study for any of the following reasons:

- Disease progression as defined in [Section 11](#).
- Patient non-compliance or request to withdraw from all therapy and follow up. Patients who withdraw from therapy only may continue to be followed for study specified follow up secondary endpoints.
- Pregnancy.
- Unacceptable toxicity that in the treating physician's discretion places the patient at risk

for future significant harm.

- Intercurrent illness that prevents continuation of therapy or follow up.

#### 4.10 Treatment Beyond Progression

Treatment beyond initial investigator-assessed RECIST 1.1-defined progression is permitted if the subject has investigator-assessed clinical benefit and is tolerating treatment, as specified in [Section 6.3](#)

#### 4.11 Duration of Study

The analysis of the primary endpoint ORR will be performed six months after the last subject's first treatment. Additional survival follow-up may continue for up to 5 years from the primary analysis. The study will end once survival follow-up has concluded.

### 5. DOSING REDUCTIONS/DOSE DELAYS

#### 5.1 Dose Reductions

##### Recommended Dose Modifications for OPDIVO (Nivolumab)

Adverse Reaction	Severity	Dose Modification
Colitis	Grade 2 diarrhea or colitis	Withhold dose a
	Grade 3 diarrhea or colitis	Withhold dose a when administered as a single agent
	Grade 4 diarrhea or colitis	Permanently discontinue when administered with ipilimumab
Pneumonitis	Grade 2 pneumonitis	Withhold dose a
	Grade 3 or 4 pneumonitis	Permanently discontinue
Hepatitis	AST or ALT > 3 - 5 x ULN or total bilirubin > 1.5 - 3 x ULN	Withhold dose a
	AST or ALT > 5 ULN or total bilirubin > 3 x ULN	Permanently discontinue
Hypophysitis	Grade 2 or 3 hypophysitis	Withhold dose a
	Grade 4 hypophysitis	Permanently discontinue
Adrenal Insufficiency	Grade 2 adrenal insufficiency	Withhold dose a
	Grade 3 or 4 adrenal insufficiency	Permanently discontinue
Type 1 Diabetes Mellitus	Grade 3 hyperglycemia	Withhold dose a
	Grade 4 hyperglycemia	Permanently discontinue
Nephritis and Renal Dysfunction	Serum creatinine > 1.5 – 6 x ULN	Withhold dose a
	Serum creatinine > 6 x ULN	Permanently discontinue

Skin	Grade 3 rash or suspected Stevens-Johnson syndrome (SJS) or toxic epidermal necrolysis (TEN)	Withhold dose a
	Grade 4 rash or confirmed SJS or TEN	Permanently discontinue
Encephalitis	New-onset moderate or severe neurologic signs or symptoms	Withhold dose a
	Immune-mediated encephalitis	Permanently discontinue
Other	Other Grade 3 adverse reaction: First occurrence	Withhold dose a
	Recurrence of same Grade 3 adverse reactions	Permanently discontinue
	Life-threatening or Grade 4 adverse reaction	Permanently discontinue
	Grade 3 myocarditis	Permanently discontinue
	Requirement for $\geq 10$ mg per day prednisone or equivalent for $> 12$ weeks	Permanently discontinue
	Persistent Grade 2 or 3 adverse reactions lasting 12 weeks or longer	Permanently discontinue

\* Toxicity was graded per NCI CTCAE v4.

a Resume treatment when adverse reaction improves to Grade 0 or 1.

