3.1.7 ECOG performance status  $\leq 1$  (see Appendix 1)

3.1.8 Prior palliative radiotherapy to non-CNS lesions must have been completed at least 2 weeks prior to treatment. Subjects with symptomatic tumor lesions at baseline that may require palliative radiotherapy within 4 weeks of first treatment are strongly encouraged to receive palliative radiotherapy prior to treatment.

3.1.9 Patients must have normal organ and marrow function as defined below:

- WBC	$\geq 1,500/\text{mcL}$
- absolute neutrophil count	$\geq 1,000/\text{mcL}$
- hemoglobin	$\geq 8.0 \text{ g/dL}$
- platelets	$\geq 75,000/\text{mcL}$
- total bilirubin	$\leq 1.5 \times \text{institutional ULN}$ (patients with Gilbert's syndrome may have serum bilirubin $\leq 3 \times \text{ULN}$ )
- AST/ALT	$\leq 3 \times \text{institutional ULN}$ ( $\leq 5 \times \text{ULN}$ in the presence of liver metastases)
- creatinine	$\leq 1.5 \times \text{institutional ULN}$ or creatinine clearance (CrCl) $\geq 40 \text{ mL/min}$ (if using the Cockcroft-Gault formula below):

*Female:*

$$\text{CrCl} = \frac{(140 - \text{age in years}) \times \text{weight in kg} \times 0.85}{72 \times \text{serum creatinine in mg/dL}}$$

*Male:*

$$\text{CrCl} = \frac{(140 - \text{age in years}) \times \text{weight in kg} \times 1.00}{72 \times \text{serum creatinine in mg/dL}}$$

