## 5.2 Dosing Delays

- In addition to the dose modifications in 6.1, any AE, laboratory abnormality or inter-current illness which, in the judgment of the investigator, warrants delaying the dose of study medication.

Subjects that have drug-related toxicities that meet the criteria for dose delay, should have both drugs (ipilimumab and Nivolumab) delayed until retreatment criteria are met.

Tumor assessments for all subjects should continue as per protocol even if dosing is delayed.

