### 5.2.3 Criteria to Resume Ipilimumab Dosing

- Subjects may resume treatment in the presence of Grade 2 fatigue.
- Subjects with baseline Grade 1 AST/ALT or total bilirubin who require dose delays for reasons other than a 2-grade shift in AST/ALT or total bilirubin may resume treatment in the presence of Grade 2 AST/ALT or total bilirubin.
- Drug-related endocrinopathies adequately controlled with only physiologic hormone replacement may resume treatment after consultation with the IND Sponsor.
- Treatment-related dose delay of ipilimumab which results in no ipilimumab dosing for  $> 12$  weeks requires ipilimumab discontinuation.
- Ipilimumab may not be resumed sooner than 6 weeks ( $\pm 5$  days) after the prior ipilimumab dose.
- In general, subjects who meet criteria to resume ipilimumab will also have met criteria to resume nivolumab, so it should be feasible to synchronize dosing of both drugs when resuming ipilimumab. In order to facilitate this, the dosing days of nivolumab and ipilimumab may be adjusted within the permitted  $\pm 5$  day window, as long as consecutive nivolumab doses are given at least 12 days apart.
- Any Grade 3 drug-related laboratory abnormality (except lymphopenia, AST, ALT, or total bilirubin or asymptotic lipase or amylase). Any Grade  $\geq 3$  drug-related amylase or lipase abnormality that is not associated with symptoms or clinical manifestations of pancreatitis does not require dose delay. The IND Sponsor should be consulted prior to resuming nivolumab in such subjects.

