## 6. ADVERSE EVENTS: LIST AND REPORTING REQUIREMENTS

This study will use the descriptions and grading scales found in the revised National Cancer Institute Common Terminology Criteria for Adverse Events (CTCAE) Version 4.0 for adverse event reporting that can be found at [http://ctep.cancer.gov/protocolDevelopment/electronic\\_applications/ctc.htm](http://ctep.cancer.gov/protocolDevelopment/electronic_applications/ctc.htm).

Information about all AEs, whether volunteered by the subject, discovered by investigator questioning, or detected through physical examination, laboratory test or other means, will be collected, recorded, and followed as appropriate.

All AEs and SAEs experienced by subjects will be collected and reported from the first dose of nivolumab, throughout the study, and will only be followed for 4 weeks unless related to the investigational agent. All SAEs will be collected for 100 days after the last dose of nivolumab. Subjects who have an ongoing AE related to the study procedures and/or medication(s) may continue to be periodically contacted by a member of the study staff until the event is resolved or determined to be irreversible by the investigator.

**Laboratory abnormalities:** Laboratory abnormalities present at the screening visit will be recorded as pre-treatment signs and symptoms. After study treatment administration, all grade 3 and 4 clinical laboratory results that represent an increase in severity from baseline will be reported as adverse events. A grade 1 or 2 clinical laboratory abnormality should be

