## 6.1 Definitions

### 6.1.1 Adverse Event

An adverse event (AE) is defined as any new untoward medical occurrence or worsening of a preexisting medical condition in a clinical investigation subject administered study drug and that does not necessarily have a causal relationship with this treatment. An AE can therefore be any unfavorable and unintended sign (such as an abnormal laboratory finding), symptom, or disease temporally associated with the use of study drug, whether or not considered related to the study drug.

BMS will be reporting adverse events to regulatory authorities and ethics committees according to local applicable laws including European Directive 2001/20/EC and FDA Code of Federal Regulations 21 CFR Parts 312 and 320.

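### The liver-test hold, resume and discontinuation rules ignore baseline, although subjects may enter above 3 x ULN for AST/ALT, or above 1.5 x ULN for bilirubin with Gilbert's syndrome

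*Combined protocol and SAP*

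**What the plan says.** **Entry.** Section 3.1.9 caps AST/ALT at 3 x ULN, raised to 5 x ULN "in the presence of liver metastases". Total bilirubin is capped at 1.5 x ULN, raised to 3 x ULN for Gilbert's syndrome.

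**Nivolumab.** The hepatitis row of the Section 5.1 table withholds the dose at "AST or ALT > 3 - 5 x ULN or total bilirubin > 1.5 - 3 x ULN" and discontinues permanently at "AST or ALT > 5 ULN or total bilirubin > 3 x ULN". The footnote on withheld doses reads "Resume treatment when adverse reaction improves to Grade 0 or 1". The same table discontinues nivolumab when a Grade 2 or 3 reaction persists for 12 weeks.

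**Ipilimumab.** The companion table in Section 5.1, under its residual category, withholds for Grade 2 and resumes at Grade 0 to 1 on low-dose steroid. It discontinues when a Grade 2 reaction lasts 6 weeks, or at Grade 3 or 4.

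**Baseline provision.** There is one, in Section 5.2.3 on resuming ipilimumab. "Subjects with baseline Grade 1 AST/ALT or total bilirubin who require dose delays for reasons other than a 2-grade shift" in those tests may restart at Grade 2. Section 5.2.2, on resuming nivolumab, has no counterpart. Its laboratory bullet lists AST, ALT and bilirubin as exceptions but never completes the rule.

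**What triggers a delay.** Section 5.2 delays both drugs for "Subjects that have drug-related toxicities that meet the criteria for dose delay". It also lets the investigator delay for any laboratory abnormality thought to warrant it. Section 6.1.1 defines an adverse event as "any new untoward medical occurrence or worsening of a preexisting medical condition in a clinical investigation subject administered study drug". Section 6 adds: "Laboratory abnormalities present at the screening visit will be recorded as pre-treatment signs and symptoms".

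**Appendix 2.** A footnote to the hepatic algorithm allows delay in place of discontinuation if AST/ALT is at most 8 x ULN or bilirubin at most 5 x ULN.

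**The concern.** The entry criteria anticipate that liver metastases, or Gilbert's syndrome, may leave a subject with raised liver tests. The dosing rules that follow do not. They are written in fixed multiples of ULN, as if every subject started near normal. A subject who enters inside the hold band has little or no room before the discontinuation line, and the resume target may lie below that subject's own starting point.

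Two things are at stake. The first is consistent management: the same laboratory value could lead to continuation, a hold or permanent discontinuation, depending on which section a site follows. The second is interpretation. Objective 1.2.1 quantifies dose interruptions and characterizes toxicity. If the rules cannot separate a drug effect from the state in which the subject entered, some hepatic holds and discontinuations will describe baseline disease rather than tolerability.

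**Working it through.** The plan states no statistical figure on this point, so there is none to reproduce. The check sets the ranges against each other, all in multiples of ULN.

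**Step 1: overlap at entry.** Inputs are Section 3.1.9 and the nivolumab table in Section 5.1.

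| Test and group | Eligible | Hold band | Overlap with hold | Overlap with discontinuation |
|---|---|---|---|---|
| AST/ALT, no liver metastases | up to 3 | above 3 to 5 | none | none |
| AST/ALT, liver metastases | up to 5 | above 3 to 5 | above 3 to 5 (whole band) | none |
| Bilirubin, general | up to 1.5 | above 1.5 to 3 | none | none |
| Bilirubin, Gilbert's | up to 3 | above 1.5 to 3 | above 1.5 to 3 (whole band) | none |

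The overlap is exact, and it is confined to the two groups given a higher entry limit.

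**Step 2: does a pre-dose value trigger a hold?** The table governs adverse reactions, and its row is hepatitis. An adverse event must be new or worsening in a subject given study drug, and screening abnormalities are recorded as pre-treatment findings. A stable value of 4 x ULN before the first dose is therefore in the band numerically but is not the event that the band regulates. The gap opens only after dosing.

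**Step 3: distance to permanent discontinuation.** For baseline b, the relative rise that reaches the AST/ALT line is 5/b - 1.

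- b = 3.1: 5/3.1 - 1 = 61%
- b = 4.0: 5/4.0 - 1 = 25%
- b = 4.9: 5/4.9 - 1 = 2%
- b = 5.0: any rise

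A move from 4.9 to 5.1 x ULN is 5.1/4.9 - 1 = 4%, and it crosses the line. For bilirubin in Gilbert's syndrome the margin is 3/b - 1, which is 100% at b = 1.5 and nothing at b = 3. Worsening of a pre-existing condition is an adverse event under Section 6.1.1, so the table can apply to such a change.

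**Step 4: can the resume rule be met?** Let c be the upper end of Grade 1 for AST/ALT. The documents do not print it. I assume c = 3, which is also where the hold band starts. A held subject who returns exactly to baseline b satisfies Grade 0 or 1 only if b is at most c. With c = 3, every subject in the above-3-to-5 group fails on returning to baseline. If c were higher, only those with b above c would fail, and at c = 5 none would. The bilirubin case is the same, with the assumption that Grade 1 ends at 1.5 x ULN.

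While such a subject waits, Section 5.1 sets limits of 6 weeks (ipilimumab, Grade 2) and 12 weeks (nivolumab, Grade 2 or 3). Section 5.2.1 adds its own limits on treatment-related delay. The Section 5.2.3 provision does not help, because it covers ipilimumab and a Grade 1 baseline only.

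**Step 5: Section 5.1 against Appendix 2.** Section 5.1 discontinues nivolumab above 5 x ULN (AST/ALT) or above 3 x ULN (bilirubin). The Appendix 2 footnote allows delay up to 8 and 5 x ULN. The two differ for AST/ALT above 5 to 8 x ULN and for bilirubin above 3 to 5 x ULN. Subjects who start near the lower end of those ranges reach the conflict soonest. The flow chart to which the footnote belongs was not in the text examined, so this rests on the footnote's wording.

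**The case against.** The best reply is that the protocol already separates baseline disease from drug effect. The table is about adverse reactions, joint delay is tied to drug-related toxicity, and screening abnormalities are set aside as pre-treatment findings. An investigator can judge a stable or slightly drifting value to be disease. In Gilbert's syndrome a cause is already known. The Section 5.1 tables are also titled as recommendations, and Appendix 2 offers delay. The affected group may be small or empty.

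Much of this stands. A reader might infer that an eligible subject at 4 x ULN must be held on day 1, so that eligibility and dosing contradict each other outright. The documents do not support that, for the reasons in Step 2. It might also be inferred that such a subject, never completing a dose of both drugs, drops out of the all-treated denominator for ORR in Section 12.3.1. That depends on a mandatory day-1 hold, which the protocol does not impose. Section 5.2 would permit a discretionary delay, but nothing shows that this would cost anyone the first dose.

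The reply does not close the gap after dosing. It then rests on attribution, and Section 6.2 makes attribution hard. Related requires that no other cause can be identified, while unrelated requires a time course that rules the drug out. A subject with liver metastases whose AST rises after dosing may fit neither. Nor does any rule say that a return to baseline counts as resolution. Appendix 2 does not settle the matter, because it disagrees with Section 5.1.

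**Conclusion.** The point holds as an unreconciled set of on-treatment rules for subjects admitted above 3 x ULN AST/ALT with liver metastases, or above 1.5 x ULN bilirubin with Gilbert's syndrome. It is neither a day-1 contradiction nor a demonstrated threat to the primary endpoint, and no effect on sample size or error rates follows from it.

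Per subject, the margin to permanent discontinuation shrinks from about 61% at 3.1 x ULN to nothing at 5 x ULN. The resume difficulty rests on the assumption that Grade 1 ends at 3 x ULN for AST/ALT and 1.5 x ULN for bilirubin. The conflict between Section 5.1 and Appendix 2 needs no such assumption. The number of subjects cannot be computed: the documents give no share with raised baseline liver tests, so any percentage applied to the 56 planned treated subjects would be a guess. It should be fixed because the change is cheap and bears on safety conduct and on objective 1.2.1.

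**What to change.** The sponsor should reconcile Section 3.1.9, both tables in Section 5.1, Sections 5.2.2 and 5.2.3, and the hepatic footnote in Appendix 2. The amended text should state:

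- how the hold, resume and permanent-discontinuation criteria apply to a subject admitted above 3 x ULN AST/ALT or above 1.5 x ULN bilirubin;
- whether a return to baseline counts as resolution, for the resume rule and for the 6-week and 12-week limits;
- which of Section 5.1 and Appendix 2 governs where they differ;
- the completed laboratory bullet in Section 5.2.2.

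Which thresholds apply, and in which direction the passages are aligned, is for the sponsor and investigators; none is proposed here. The cost is amendment wording, with no change to the sample size or the planned analyses.
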